Hypotheses will be tested using intent-to-treat (ITT) linear mixed effect analyses. Specifically, differences in outcome measures from pre-treatment through the study medication phase will be estimated using linear mixed effects regression of outcome (the dependent variable) on treatment by study visit interaction (the independent fixed effects). Study visit will be modeled as categorical (post- vs. pre-treatment). Study participant will be modeled as a random effect. Model results will be summarized with estimated marginal means at pre- and post-treatment for each treatment group, within-group mean change from pre-treatment and mean difference in change by group. The latter set of means will also be presented as standardized effect sizes calculated using the standard deviation of the outcome at baseline as the denominator. Hypothesis testing for the overall difference in change in outcome by treatment will be carried out using the likelihood ratio test for the significance of the study visit by treatment interaction term. All means will be accompanied by standard errors, and all mean differences will also be presented with 95% confidence intervals (CIs), which will be adjusted for the four sets of differences estimated corresponding to the four treatment groups using the single-step method.

Exploratory analyses will be carried out to separate the effect of the treatment from the effect of the pretreatment levels of each outcome on the estimates of post-treatment change in outcomes by adding a pretreatment outcome by visit interaction term to the model. Descriptive analyses will be carried out to summarize clinical outcomes at the last week of study. Lower risk drinking will be defined using NIAAA guidelines; for men this means exceeding neither 14 drinks per week nor 4 drinks per day and for women this means exceeding neither 7 drinks per week nor 3 drinks per day. The number of abstinent drinking days and the number of participants who are completely abstinent during the last week will also be computed. Additionally, both the raw mean PDDs and PHDDs will be computed for each week of study medication and plotted by group to illustrate changes over time in these outcomes. Type 1 error will be set at .05 for each outcome. Analyses will be carried out using R 3.6.2, and the packages lme4, emmeans and tidyverse.

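### The exploratory baseline-adjusted model, as written, regresses pre-treatment values on themselves and can report standard errors that are too small; ANCOVA would be a better primary analysis than raw change

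*Combined protocol and SAP*

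**What the plan says.** All of this is in the Statistical Analysis Plan section.

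- **Primary model.** "Hypotheses will be tested using intent-to-treat (ITT) linear mixed effect analyses". The outcome is regressed on treatment by visit, visit is a two-level factor (pre, post), and "Study participant will be modeled as a random effect". Pre-treatment values are therefore responses, with a separate pre-treatment mean for each arm.
- **Primary test.** It is the "likelihood ratio test for the significance of the study visit by treatment interaction term", which has 3 degrees of freedom with four arms. Type 1 error is 0.05 per outcome.
- **Results reported.** They include "estimated marginal means at pre- and post-treatment for each treatment group", with SEs for means and confidence intervals for differences.
- **Baseline adjustment.** This is exploratory only. To separate the treatment effect from the effect of pre-treatment level "on the estimates of post-treatment change in outcomes", the model is extended "by adding a pretreatment outcome by visit interaction term to the model". No sentence removes the pre-treatment rows, limits the term to post-treatment rows, or names a test for this analysis.
- **Missing Visit 8.** There is no rule on whether such participants keep their pre-treatment row.

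The baselines are already collected: Form-90 covers the three months before medication, and the Study Instruments table lists PACS at V1, V2 and V8.

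**The concern.** There are two points of different weight.

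**A. Primary model (a recommendation, not an error).** Comparing raw change uses the baseline less efficiently than adjusting for it. With about 30 participants per arm, the primary test may give up precision that costs almost nothing to recover.

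**B. Exploratory model (an error if fitted as written).** Crossing the pre-treatment value with a two-level visit factor gives a baseline slope at the pre visit as well as at the post visit. The pre-treatment rows then have response and covariate identical, so they carry no residual but still count as observations. The one analysis meant to separate treatment from baseline would overstate its precision, and missing Visit 8 data would not widen its SE for change as they should.

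**Working it through.** **Inputs.** 120 are to be randomised (Participants and Recruitment) to four conditions (Randomization). The allocation ratio is not stated, so 30 per arm is assumed. The documents give no power, SDs, pre-post correlation (rho), or dropout after randomisation. The only sample-size arithmetic that can be reproduced is recruitment: 240 - 70 - 50 = 120. Below, rho, the post/pre SD ratio r and the missing fraction are assumptions shown over a range.

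**A1. Precision.** With pre SD 1, the variance of change is 1 + r^2 - 2·rho·r and the ANCOVA residual variance is r^2(1 - rho^2). Their ratio (ANCOVA / change) is:

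| r | rho 0.3 | rho 0.5 | rho 0.7 |
|---|---|---|---|
| 0.7 | 0.42 | 0.47 | 0.49 |
| 1.0 | 0.65 | 0.75 | 0.85 |
| 1.25 | 0.78 | 0.89 | 0.98 |
| 1.5 | 0.87 | 0.96 | 0.998 |

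Example at r = 1, rho = 0.5: 0.75 / 1.00 = 0.75.

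**A2. Power of the 3-df test at rho 0.5.** One drug shifts two of the four arms by 0.5 baseline SD. The noncentrality is 120 × 0.25^2 / variance = 7.5 / variance. At r = 1 it is 7.5 for change and 7.5 / 0.75 = 10 for ANCOVA. Noncentral F with 116 and 115 denominator df gives, change to ANCOVA:

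| r | effect 0.5 pre SD | effect 0.5 post SD |
|---|---|---|
| 0.7 | 0.72 to 0.97 | 0.40 to 0.75 |
| 1.0 | 0.61 to 0.75 | 0.61 to 0.75 |
| 1.25 | 0.48 to 0.53 | 0.69 to 0.75 |
| 1.5 | 0.37 to 0.38 | 0.73 to 0.75 |

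**A3. Size of the planned primary test.** With complete data the likelihood ratio statistic is 120·log(RSS0/RSS1) on change (random-intercept variance above 0). It exceeds the 3-df critical value when F(3,116) > 2.60, which has probability 0.0554 at any r. With Visit 8 missing completely at random, simulation (normal outcomes, rho 0.5, 5,000 to 10,000 runs per cell, Monte Carlo SE about 0.002 to 0.003) gave:

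| r | 10% missing | 20% | 30% |
|---|---|---|---|
| 0.7 | 0.051 | 0.047 | 0.039 |
| 1.0 | 0.056 | 0.056 | 0.057 |
| 1.25 | 0.059 | 0.068 | 0.072 |
| 1.5 | 0.063 | 0.074 | 0.090 |

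The drift when r differs from 1 comes from the random intercept's single residual variance. The ANCOVA F test stayed at 0.047 to 0.054 throughout.

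**B1. Algebra of the exploratory model.** Let p be the fraction with Visit 8 and s^2 the ANCOVA residual variance. Pre rows fit exactly, so all residual sum of squares comes from the 120p post rows but is spread over 120(1 + p) rows. The model's residual variance is about s^2·p/(1 + p), with random-intercept variance about 0.

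- Post-visit arm difference: the model variance is [s^2·p/(1 + p)]·2/(30p), against the correct 2s^2/(30p). The SE ratio is sqrt(p/(1 + p)), or 0.707 at p = 1.
- Difference in change, all participants kept: the model variance is [s^2·p/(1 + p)]·2·[1/30 + 1/(30p)] = 2s^2/30, against the correct 2s^2/(30p). The SE ratio is sqrt(p): 1 with complete data, and 0.949, 0.894, 0.837 at 10%, 20%, 30% missing.

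**B2. Check in lme4** (REML, 300 fits per cell, r = 1, rho 0.5, so s^2 = 0.75).

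- The largest pre-row residual was 1.2e-7, and the change estimate equalled the ANCOVA estimate to 2e-15.
- Complete data: SE of a post mean was 0.112 against 0.158, and of a post-visit arm difference 0.158 against 0.224 (both ratio 0.707). In 2,000 simulated trials at each of rho 0.5 and 0.7, nominal 95% intervals for the post-visit difference covered about 84 to 85%. SE of the difference in change was 0.224 against an empirical SD of 0.224, which is correct.
- With 10/20/30% missing and rows kept: SE of change stayed at 0.223/0.224/0.223 while ANCOVA gave 0.236/0.252/0.268 (ratio 0.95/0.89/0.83).
- lme4 raised its singular-fit flag in only 73 to 79% of fits (R 4.3.3, lme4 1.1.37; the plan names R 3.6.2).

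**B3. If the primary likelihood ratio test were reused here.** Null rejection was 0.062 with complete data. At 10/20/30% missing it was 0.087/0.118/0.169 with rows kept and 0.060/0.062/0.064 with those participants dropped. The excess due to the defect is about 0.03/0.06/0.11, and none if they are dropped. A check with bounded outcomes (90 pre and 42 post days, r 1.17, rho 0.55) gave 0.062 with complete data and 0.080/0.116/0.178 with rows kept.

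**The case against.** The strongest reply has four parts.

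1. **Comparing change between randomised arms is accepted and matches the plan's stated target.** This stands. Part A is therefore a recommendation, and its gain cannot be fixed from the documents. In the bounded check above the variance ratio is 0.88, an SE reduction of about 6%.
2. **Part B depends on conditions.** The slope must be fitted at the pre visit. For the SE of change, participants without Visit 8 must be kept. For the rejection rates, the primary test must be reused. For the 29% error, post-visit quantities must be reported. These conditions are real. However, adding the term to the same model is the natural reading, the intention-to-treat statement makes keeping everyone plausible, and the plan promises SEs for all means. If baseline entered on post rows only, the SEs would not be too small (simulated coverage about 94 to 95%).
3. **PACS may differ.** If V1 supplied the covariate and V2 the pre row, the fit would not be exact. With an assumed V1-V2 correlation of 0.8 and 20% missing, rejection was about 0.09 rather than 0.12. The problem is reduced, not removed.
4. **Changing a primary test is more than a text edit once outcomes have been seen.** Maintaining the Study Blind lets the investigators break the blind for interim analyses. This is fair, and bears on the timing and justification of the change.

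The singular-fit rate may also differ in the software version that the plan names.

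**Conclusion.** The concern holds, with its limits.

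**Primary test.** It is valid with complete data (size 0.055). If Visit 8 values are missing and the SDs differ, its size moved to between 0.039 and 0.090 in the cases examined. ANCOVA estimates the same difference with equal or smaller large-sample variance. The gain runs from large (ratio 0.42) to almost none (0.998), depending on a correlation and an SD ratio that the documents do not give.

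**Exploratory model as written.** Post-visit SEs are about 29% too small even with complete data. The SE of the difference in change is too small, by about the square root of the completion fraction, only if participants without Visit 8 are kept. Point estimates of the difference in change are unaffected. The analysis is exploratory, so the confirmatory conclusion does not rest on it. It should still be corrected, because adjusting for baseline is its whole purpose.

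**What to change.** - **Primary (recommended), for each outcome:** ANCOVA of the post-treatment value on treatment (four levels) and the pre-treatment value, with the 3-df test.
- **Alternative that keeps participants without Visit 8:** a two-visit model with one common pre-treatment mean and an unstructured 2 × 2 covariance. It gave the same arm differences as ANCOVA on the four data sets tried. Do not pair the common mean with the planned random intercept: its complete-data null rejection at rho 0.5 is 0.009 at r = 0.7, 0.104 at 1.25 and 0.144 at 1.5.
- **Exploratory model:** delete it, or refit it with post-treatment rows only as the response.
- **State in the plan** which visit supplies the pre-treatment PACS and how participants without Visit 8 are handled.
- **Keep the planned change model** as a sensitivity analysis, and report observed pre-treatment means descriptively.

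**Cost.** A few lines of text and code, one degree of freedom and no new data. ANCOVA uses only participants with Visit 8 and gives no modelled pre-treatment arm means; observed means replace them. The two-visit alternative needs a routine with visit-specific variances (for example nlme gls), which is outside the listed packages. Make the change before any unblinded look at outcomes, or document and justify it if one has occurred.

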provocative reading material and puzzle books prior to completing the second induction, the procedures of which parallels the first.

Study Medications

Prazosin: Prazosin HCl or identical matched placebo capsules are dispensed as 1, 2, and 4 mg capsules prepared by Kelley-Ross Pharmacy, a compounding pharmacy in Seattle. A 25mg riboflavin trace will be added to each capsule to evaluate medication compliance.

Naltrexone: 50 mg naltrexone or identical matched placebo capsules prepared by Kelley-Ross Pharmacy (tablets are ground and then compounded with the 25mg riboflavin trace).

Procedures for Maximizing Research Integrity

Maintaining the Study Blind: Only the VAPSHCS research pharmacist will have access to the randomization schedule, and she will have no contact with study participants. The blind may be broken by the PIs in case of safety concerns and for the purposes of interim analyses, but the information will not be shared with study staff except in the event of clinically significant safety concerns.

Maximizing Retention: We update contact information at each clinical and assessment visit. Participants will be paid \$15 for each of the two blood draws.

Study Instruments

Study Construct/ Variables	Study Phase	Purpose
Inclusion/Exclusion Criteria and Blocking Factors		
Demographic information	V1	sample description, blocking (gender)
Medical history interview	V1	exclusion
Medical Exam	V1, V8	exclusion; safety
Lab values MINI International Psychiatric Interview (DSM-V AUD & SUD onset of drinking and alcohol problems as well as recent drinking; DSM-IV Psychosis; suicidality, homicidality)	V1, V8 V1	exclusion; safety inclusion and exclusion
Alcohol use goal (embedded in MINI AUD)	V1	inclusion, blocking, treatment moderator
Desires for Alcohol Questionnaire (DAQ)	V2, V8	, outcome
Life Events Checklist	V1, V8	blocking
Penn Alcohol Craving Scale	V1, V2, V8	inclusion
Clinician-Administered PTSD Scale For DSM-5 (CAPS)	V1, V8	blocking, treatment moderator (Aim 3)
Tracking		
Contact form	V1-V7	retention
Primary Outcomes		
Alcohol Biomarker (Peth)	V1, V8	outcome
Alcohol Craving (DAQ)	V8	outcome (Aim 2)
Alcoholuse	V8	outcome (Aim 2)
Reward Craving for Craving Inductions from DAQ	V8	outcome (Aim 1)
Relief Craving for Craving Inductions from DAQ	V8	outcome (Aim 1)
Hypothesized Moderators		
State Trait Anxiety	V1, V8	moderation (Aim 3)
Anxiety Sensitivity Inventory	V1, V8	moderation (Aim 3)

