Sensitivity to Reward/Punishment Scale	V1, V8	moderation (Aim 3)
PHQ-9 Depression	V1-V8	moderation (Aim 3); safety
Family History of AUD	V2	moderation (Aim 3)
Drinking Motives (Card Sort)	V2, V8	moderation (Aim 1)
Secondary Measures (Descriptive and/or Explorate	ory)	

AUDIT	V1	sample description		
Drinking Motives Questionnaire	V1, V8	sample description		
Obsessive Compulsive Drinking Scale	V1, V2, V8	sample description		
Form-90 (alcohol)	V2, V8	sample description and outcome		
Positive and Negative Mood States	IVR, V8	sample description		
Barrett Impulsivity Scale	V2, V8	sample description		
Stroop	V2, V8	sample description		
PROMIS Pain Impact	V2 – V8	sample description		
PROMIS Sleep quality	V2 – V8	sample description		
PROMIS Wake Disturbance	V2 – V8	sample description		
PROMIS General Distress; Anxiety	V2 – V8	sample description		
Important People Inventory	V2, V8	sample description and possible moderator		
Craving Induction Preparation				
Script Preparation Form	V2	provide details for craving inductions		
Medication Management / Safety Checks				
Adverse Events Checklist and Vital Signs	All	clinical data for medication management		
PHQ-9 Suicide item (#9)	All Phone Calls	safety		

Data Safety Monitor/Research Monitor

In accordance with DODI 3216.02, the research monitor, [name], has the authority to stop this research protocol in progress, remove individual human subjects from the research protocol, and take whatever steps are necessary to protect the safety and well-being of human subjects until the IRB can assess his report. [name] is responsible for promptly report his observations and findings to the IRB or other designated official. He may also have direct contact with study participants should it be necessary to evaluate their safety and to make recommendations for any needed care or actions.

Data Management

[name], M.S., a biostatistician from the University of Washington, will analyze the study data. Because [name] is not a VA employee, the study data will be temporarily transferred to her laptop for analysis. [name] will have the study data for one year. After one year, [name] will delete them from her laptop. All data transfers will be made using methods approved by the VA Privacy Office and Information Security Office.

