The transferred data will not have any identifying information connected with them. They will be raw data numbers only identified by a study code number. Inadvertent disclosure of any of these data will not have any impact on participants, as a third party would not be able to discern what the data are. The study crosswalk, the bridge between the study code and participant's name, will be kept in the project folder in the VA secure network (\\R01PUGHSM03.R01.MED.VA.GOV\Research\[name]\IVR_Studies\00623 (AA-PaN Study)\11 - Tracking & Databases) and will not be shared with [name].

Statistical Analysis Plan

Statistical analysis will focus on three primary outcomes and a secondary outcome (average drinks per drinking day). The three primary outcomes are Percent Drinking Days (PDD), Percent Heavy Drinking Days (PHDD), and craving scores from PACS. The Form-90 will be used to gather drinking data for the three months prior to receipt of study medication as well as the six-weeks of study medication. This information will be used to compute PDD, PHDD, and average drinks per drinking day. Heavy drinking is defined as five or more drinks or four or more drinks in a day for men and women, respectively.

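### The Study Instruments table and the Statistical Analysis Plan give two incompatible lists of primary outcomes; the interim-analysis permission and the status of the .05 per outcome also need a sentence each

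*Combined protocol and SAP*

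**What the plan says.** **Primary outcomes in the SAP.** The Statistical Analysis Plan states: "The three primary outcomes are Percent Drinking Days (PDD), Percent Heavy Drinking Days (PHDD), and craving scores from PACS". The drinking outcomes come from the Form-90: "This information will be used to compute PDD, PHDD, and average drinks per drinking day". Average drinks per drinking day is the one secondary outcome.

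**Primary outcomes in the Study Instruments table.** The Primary Outcomes block has five rows: PEth, alcohol craving by the DAQ (Aim 2), alcohol use (Aim 2), reward craving for the inductions (Aim 1), and "Relief Craving for Craving Inductions from DAQ" (Aim 1). "Penn Alcohol Craving Scale" is in the inclusion/exclusion and blocking block. The Form-90 is under Secondary Measures, but its purpose entry includes use as an outcome.

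**Interim analyses.** Under Maintaining the Study Blind, the PIs may break the blind for safety and, listed separately, for interim analyses. What they learn is kept from study staff unless there is a clinically significant safety concern. The SAP does not mention an interim analysis.

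**Error rate.** The SAP says "Type 1 error will be set at .05 for each outcome". Its only multiplicity adjustment applies to the confidence intervals, which are "adjusted for the four sets of differences estimated corresponding to the four treatment groups using the single-step method". That covers treatment groups within an outcome, not the set of outcomes.

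**The concern.** A reader of the final report has to know which outcomes the trial was set up to answer. With two lists, a result on PEth, on DAQ craving or on PACS could be called primary or not, depending on which part of the document is cited. The conflict reaches the main question: the title and Aim 1 concern script-induced craving, and the SAP contains no analysis of it.

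The other two parts bear on how far any claim can be trusted. If the PIs may see unblinded interim data and nothing more is written, a reader cannot tell whether efficacy was examined early. And with three primaries at .05 each and no statement of what counts as success, a reader cannot tell whether one significant result out of three would be presented as a positive trial.

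**Working it through.** **1. The two lists side by side** (Study Instruments table against Statistical Analysis Plan)

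| Outcome | Instruments table | SAP |
|---|---|---|
| PEth | Primary; V1, V8 | Absent |
| DAQ craving | Primary (Aim 2); V8 | Absent |
| Reward craving, induction | Primary (Aim 1); V8 | Absent |
| Relief craving, induction | Primary (Aim 1); V8 | Absent |
| Alcohol use | Primary (Aim 2); V8; no instrument named | PDD and PHDD, from the Form-90 |
| PACS | Inclusion block; V1, V2, V8 | Primary |

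One row can be matched. The Form-90 is collected at V2 and V8 and is listed partly as an outcome, so PDD and PHDD fit the alcohol use row. The other five rows do not match. PEth has a baseline and a final value, so the SAP's pre/post model could take it. The induction scores could not be analysed that way: the inductions take place only at the final visit, and the model's visit factor is post- against pre-treatment.

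**2. Interim look**

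The documents give no number, timing, endpoint or boundary, so there is no stated figure to reproduce. *Assumption:* one unadjusted efficacy look that could support a claim, plus the final analysis, both at .05. The test is the visit-by-treatment likelihood ratio test. With four groups and two visits it has (4 − 1) × (2 − 1) = 3 df. Simulated error for one outcome:

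- look at 25% of the information: .092
- look at 50%: .085
- look at 75%: .075

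**3. Three outcomes at .05**

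*Input from the SAP:* three primaries, .05 each. *Assumptions:* any one success is enough, final analysis only, and the correlations below (PDD–PHDD / each with PACS), which the documents do not give.

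- Independent: 1 − .95³ = 1 − .857375 = .143
- .7 / .4: .125 (simulated)
- .9 / .6: .107 (simulated)
- .95 / .6: .102 (simulated)
- Upper bound for any correlation: 3 × .05 = .15

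Shared Form-90 data can raise only the PDD–PHDD correlation. If those two were identical and PACS independent, the result would be 1 − .95² = .0975. A value near .08 (.082 at .95 / .9) needs PACS correlated about .9 with both drinking outcomes, and nothing in the documents supports that.

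**4. Power cost of a Holm rule**

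The documents state no power, so 80% at .05 is assumed. For a 3-df test this needs noncentrality 10.90. At the first Holm step, .05/3 = .0167, the same noncentrality gives power .66. Restoring .80 needs 14.05, and 14.05 / 10.90 = 1.29, that is, 29% more information.

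**The case against.** **The .05 per outcome is a declared choice.** This stands. The most natural reading of the sentence is that each outcome is its own question. On that reading, or if all three must succeed, there is no inflation. A reader might infer that the plan's error rate is really .14, or that the stated .05 is breached. The documents support neither: they contain no claim that one success suffices.

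**The drinking outcomes are not demoted.** This also stands. From the Form-90's place under Secondary Measures, a reader might infer that PDD and PHDD are secondary in the table. The Form-90's purpose entry and the alcohol use row make that reading unsafe.

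**PACS may have been intended as an outcome.** This stands in part. Screening needs PACS only at V1, yet it is repeated at V8, where it cannot serve inclusion, and its purpose cell may have lost text in extraction. But whatever that cell says, PACS is outside the primary block, and the craving measure inside the block is the DAQ.

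**The interim clause is only permissive.** This stands. A reader might infer that an efficacy look was planned or made. The text says only that the blind may be broken. A safety or descriptive look would spend no alpha, and study staff are shielded. The shield does not cover the PIs, however, and the SAP does not say what kind of look is meant.

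None of these points explains why PEth, DAQ craving and the induction outcomes are called primary in one place and are missing in the other.

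**Conclusion.** The conflict between the two primary lists is documented and needs no assumption: four outcomes headed primary in the table have no place in the SAP, and one SAP primary is outside the table's primary block. It is the main point and should be corrected. The documents do not show when or why the lists diverged, so an inference that outcomes were switched after results were seen is not supported.

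The interim permission is a real gap, but its effect is conditional. An error of about .075 to .092 per outcome applies only if there is one unadjusted efficacy look that could support a claim.

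The error-rate point is also conditional. If any one of the three SAP primaries may carry an overall claim, the chance of at least one false positive is about .10 to .14, roughly two to three times .05, under assumed correlations. If the outcomes are read separately, there is nothing to correct beyond saying so.

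**What to change.** 1. **One primary list.** Before unblinding, reconcile the Study Instruments table and the Statistical Analysis Plan. Either give the two induction outcomes, PEth and DAQ craving an analysis in the SAP, or state that they are no longer primary. State which craving measure is primary, and name the instrument for alcohol use. The induction outcomes would need a model of their own. If the data are already unblinded, label the choice post hoc and report every outcome on either list. Cost: wording, plus a short analysis section if the induction outcomes stay primary.

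2. **Interim analyses.** Remove the interim-analysis permission from Maintaining the Study Blind and state that there is no efficacy interim. If the sponsor wants one, state its purpose, timing and boundary, and keep the PIs blinded to it. If an interim unblinding has already happened, report when it happened, who was unblinded and what was seen. Removing the permission costs no power.

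3. **Status of the .05.** Add one sentence. It may say that each outcome is interpreted separately with no overall claim, which costs no power. Or it may name the rule that governs an overall claim: a single primary or a fixed sequence keeps the full .05 for the first outcome, while Holm takes an assumed 80% power to 66% at its first step. With 120 to be randomized, the extra 29% of information is not available, so under Holm the lower power would have to be accepted.
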